5.1.2. Handling of Missing Data

All data will be analyzed as they were collected in the database. In general, missing data, unless noted otherwise, will not be imputed. However, imputation of missing AE ([Section 4.2.1](#)) and concomitant medication ([Section 5.2.6](#)) onset and stop dates will be used to determine the status of each AE and the prior/concomitant status of each medication.

G1 Therapeutics, Inc.
Clinical Study Protocol G1T38-03
Statistical Analysis Plan

For demographic and baseline characteristics, each variable will be analyzed and/or summarized using available data. For continuous variables, subjects with missing data will be excluded from analyses for which data are not available. For categorical variables, a “Missing” category will be added for subjects with missing data.

5.1.3. Study Days and Visit Windowing

Study Days Relative to First Administration of Study Medication on Cycle 1 Day 1

Study Day 1 is the day continuous daily doses of G1T38 and osimertinib commences.

Negative Study Days occur prior to first administration of study medication on C1D1; and positive Study Days are those after the first administration of study medication on C1D1—e.g., Study Day -1 is the day immediately preceding the first administration of study medication on C1D1, Study Day 2 is the day immediately following the first administration of study medication on C1D1.

Visit Windowing

It is expected that there will be a variation between patients in the actual number of study days from the start of administration of study drug on C1D1 – defined as Day 1 – to the dates that the scheduled visit occurs. To handle this, for tables and figures where data are grouped by visit, assessments will be categorized using visit windows based on study days. The visit-window mapping is described in [Table 10](#) for Part 1 for safety assessments. Visit-based summaries will be based on the windowed visits. All data, whether or not within the visit windows, will be presented in by patient listings.

For windowed visit between the treatment start date (i.e., Cycle 1 Day -16) through post-treatment visit, if more than one visit occurs during a visit window, the visit closest to the scheduled day will be assigned to the windowed visit. If two visits are equidistant from the scheduled day, the later visit will be assigned to the windowed visit.

For a patient who prematurely discontinues treatment, the visit will be slotted accordingly. The window for post-treatment visit will be from the "last dose date + 30 to date of last assessment prior to the start of survival follow-up".

Table 10 Windowing Algorithm for Part 1						
Visit	Scheduled Day	Vital Signs	Clinical Chemistry	Hematology	Urinalysis and ECOG	ECG
Screening	NA	-37 to -17	-37 to -17	-37 to -17	-37 to -17	-37 to -17
C1D-16	-16	-16	-16	-16	-16	-16
C1D-2	-2	-15 to -1				-15 to -1
C1D1	1	1 to 3	-15 to 3	-15 to 3	-15 to 3	
C1D8	8			4 to 11		
C1D15	15	4 to 21	4 to 21	12 to 18		
C1D22	22			19 to 25		
C2D1	29	22 to 35	22 to 35	26 to 32	4 to 42	1 to 42

G1 Therapeutics, Inc.
 Clinical Study Protocol G1T38-03
 Statistical Analysis Plan

C2D8	36			33 to 39		
C2D15	43	36 to 49	36 to 49	40 to 46		
C2D22	50			47 to 53		
C3D1	57	50 to 70	50 to 63	54 to 63	43 to 70	43 to 70
C3D15	71		64 to 77	64 to 77		
C4D1	85	71 to 98	78 to 91	78 to 91	71 to 98	
C4D15	99		92 to 105	92 to 105		
C5D1	113	99 to 126	106 to 126	106 to 126	99 to 126	
CYD1 ^a	28(Y-1)+1	28(Y-1)-13 to 28(Y-1)+14	28(Y-1)-13 to 28(Y-1)+14	28(Y-1)-6 to 28(Y-1)+7	28(Y-1)-13 to 28(Y-1)+14	28(Y-1)-13 to 28(Y-1)+14
CYD15 ^a	28(Y-1)+15			28(Y-1)+8 to 28(Y-1)+21		
Post-treatment visit	Last dose date + 30 days					

Absolute neutrophil counts will be monitored weekly for the first 8 weeks (2 cycles), then every 2 weeks for the next 2 cycles. Beginning with Cycle 5 Day 1, patients with stable \leq Grade 2 hematologic parameters may have hematology monitored monthly on Day 1 of each cycle; patients that do not meet this criteria will continue to have every other week assessment of hematologic parameters.

Clinical chemistry will be monitored every 2 weeks for the first 4 cycles. Beginning with Cycle 5 Day 1, clinical chemistry will be monitored monthly on Day 1 of each cycle.

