9. STUDY SCHEDULE

The procedures and assessments to be performed during the study are outlined in Table 9-1 (Part 1) and Table 9-2 (Part 2).

Version: 4.0, dated 02 September 2019 Page 53 of 103

 Table 9-1
 Schedule of Assessments for Part 1

						Т	reatment l	Phase					
			Cycle 1			Cycles	s 1 and 2			3 and Every e Thereafter		Post-	
Assessment	Screen -ing	Day -16	Day -14 (+ 1)	Day -2 (± 1)	Day 1 (+ 2)	Day 8 (± 2)	Day 15 (± 2)	Day 22 (± 2)	Day 1 (± 3)	Day 15 (± 3) [as required in Cycle 5 and beyond]	Discon- tinuation	Treat- ment Visit (+10)	Details Provided in Section
Informed consent	X												9.1
EGFR mutation status	X												
Medical/surgical history	X												
Archival tumor sample (if available)	X												10.3
Demographics and baseline characteristics	X												10.6.3
Vital signs	X	X		X	X		X		X		X	X	10.6.3
Inclusion/ exclusion criteria	X												7.1
Physical examination, including weight	X											X	10.6.4
Symptom-directed physical examination		X			X		X		X	X	X		
Height	X												10.6.3
Full ophthalmic examination	X				Perform i	f the patier	nt experience	ces any visu	ıal sympto	ms			10.6.6
ECOG performance status	X	X			X				X		X	X	7.1.1
Blood sample for cell-free DNA		Х			X (Cycle 2 only)		X (Cycle 1 only)		X (odd Cycles only)			X	10.2

						1	reatment l	Phase					
			Cycle 1			Cycles	s 1 and 2			3 and Every e Thereafter		Post-	
Assessment	Screen	Day -16	Day -14 (+ 1)	Day -2 (± 1)	Day 1 (+ 2)	Day 8 (± 2)	Day 15 (± 2)	Day 22 (± 2)	Day 1 (± 3)	Day 15 (± 3) [as required in Cycle 5 and beyond]	Discon- tinuation	Treat- ment Visit (+10)	Details Provided in Section
Pregnancy test	X	X	(+1)	(±1)	(+2)	(±2)	(±2)	(±2)	(±3)	and beyond	tinuation	X	Table 10-5
Clinical chemistry	X	X			X		X		X	X	X	X	and 10.6.2; (includes
Hematology	X	X			X	X	X	X	X	X	X	X	Cycle 5 and beyond
Urinalysis	X	X			X				X		X	X	decrease in
Cystatin C		X				C	only if serur	n creatinine	e > ULN				monitoring frequency)
ECG	X	X		X	X (Cycle 2 only)				X		X	X	10.6.5
Echocardiogram/ MUGA scan	X								cycle day	and every third (12 weeks ± 7 s) thereafter			10.6.7
Tumor assessments (RECIST v1.1)	X						ven cycle (± very third cy				X		
CT/MRI brain	X									1 if indicated; tive to C1D1	X		10.1
Optional tumor biopsy at time of progression											X		10.4
Enrollment		X											9.1
Dispense study drug		X			X				X				8.1.3
Dose with G1T38 (Part 1 only)		X	X Daily dosing with G1T38 beginning on Cycle 1 Day 1										

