4.2.1. Adverse Events (AEs)

The severity (toxicity grade) of AEs will be graded according to the National Cancer Institute (NCI) Common Terminology Criteria for Adverse Events (CTCAE), Version 4.03.

All AEs will be classified by System Organ Class (SOC) and Preferred Term (PT) according to the Medical Dictionary for Regulatory Activities (MedDRA) version 23.0.

Treatment-emergent AEs (TEAEs) are defined as any AE occurring on or after the first dose of study drug (i.e., C1D-16) until 30 days after the last dose of study drug (G1T38 or Osimertinib, which is later) but prior to the start of survival follow-up. For AEs with an incomplete or unknown/not reported onset date, the imputed onset date will be used to determine if the AE is treatment-emergent.

AEs with onset dates that are partially/completely missing will be imputed as follows:

If the start date has month and year but day is missing,

- If the month and year is the same as the first dose date, then the first dose date will be used, otherwise, the first day of the month will be used

G1 Therapeutics, Inc.
Clinical Study Protocol G1T38-03
Statistical Analysis Plan

If the start date has year, but day and month are missing,

- If the year is the same as the first dose date, then the first dose date will be used, otherwise 1st Jan will be used

If the start date of an event is completely missing, then AE start date is imputed with the first dose date.

After imputation, the imputed start date will be compared with the complete or imputed (if missing or partial) AE stop date. If the imputed start date is later than the stop date, the stop date will be used as imputed start date instead.

Imputation rules for missing or partial AE stop date are defined below:

- If the stop date has month and year but day is missing, the last day of the month will be imputed
- If the stop date has year, but day and month are missing, the 31st of December will be imputed
- If the AE end date is completely missing, the last dose date +30 days will be used as the AE end date.

After the imputation, the imputed AE stop dates will be compared against the date of death, if available. If the date is later than the date of death, the date of death will be used as the imputed date instead.

The following durations will be derived for an AE, AE leading to death, AE leading to discontinuation of any study drug as appropriate and will be displayed in the corresponding AE listings. Cycle 1 Day -16 is used for date of first dose.

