4.2.5. Electrocardiograms (ECGs)

All patients will have three 12-lead electrocardiograms (ECGs) performed at the visits indicated in Table 9-1 of the protocol.

G1 Therapeutics, Inc.
 Clinical Study Protocol G1T38-03
 Statistical Analysis Plan

Part 1 Triplicate ECG requirements are as follows:

Cycle and Day	Time Points
Screening	Anytime during visit (one set of 3 ECGs)
Cycle 1 Day -16	Predose and at 2 and 6 hours (\pm 15 minutes) after the G1T38 dose
Cycle 1 Day -2	Predose and at 2 and 6 hours (\pm 15 minutes) after the G1T38 dose
Cycle 2 Day 1 and Day 1 of each cycle thereafter	Anytime during visit (one set of 3 ECGs)

Collected QTcB and QTcF will not be summarized in tables, but will instead be derived from the QT and Heart Rate (HR) based on the following formulas:

- (i) Bazett (obtained in milliseconds): $QTcB = QT / (RR^{1/2})$
- (ii) Fridericia (obtained in milliseconds): $QTcF = QT / (RR^{1/3})$

where QT is measured in milliseconds, RR is derived in seconds from HR in beats-per-minute (bpm):

$$RR \text{ (seconds)} = 60 / (\text{HR in beats-per-minute}).$$

If QT and/or HR is missing, then QTcB and QTcF will be left as missing.

ECG potentially clinically significant criteria are listed in [Table 9](#) below:

Table 9 ECG Potentially Clinically Significant Criteria

ECG Parameter	Criterion- Observed Value	Criterion-Change from Baseline
Heart Rate	>120 bpm	n/a
	<50 bpm	n/a
PR Interval	≥ 210 ms	n/a
RR Interval	>1200 ms	n/a
	<500 ms	n/a
QRS Interval	≥ 120 ms	n/a
	≤ 50 ms	n/a
QT Interval	≥ 500 ms	n/a
	≤ 300 ms	n/a
QTcB, QTcF Intervals	≥ 500 ms	increase ≥ 30 and < 60 ms
	≥ 480 and < 500 ms	increase ≥ 60 ms
	≥ 450 and < 480 ms	decrease ≥ 30 ms and < 60 ms
	>300 and < 450 ms	decrease ≥ 60 ms
	≤ 300 ms	

The average value is used for the criteria if multiple assessments are planned at a nominal timepoint

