Safety assessments (other than AEs) during treatment period is defined as assessment that is evaluated between the date of first dose of study drug and the date of last dose of study drug + 29 days. Assessments occur on or after last dose of study drug + 30 days will be counted as assessments during post-treatment period. If start date of survival follow up is available, assessments during post-treatment period should occur prior to the start of survival. If the last dose date of study drug is missing, any assessment/event occurring after the start of study drug will be considered as during treatment period.

All data will be listed for all enrolled patients.

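### SAP Table 10 labels first-dose-day safety data as Screening when Cycle 1 Day 1 is late, and its Cycle 5 Day 1 hematology window does not match its own two-weekly formulas (by-visit displays only)

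*SAP*

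**What the plan says.** **Day count.** SAP 5.1.3 fixes the origin: "Study Day 1 is the day continuous daily doses of G1T38 and osimertinib commences". Negative days count back from that date, and there is no Day 0. For displays by visit, "for tables and figures where data are grouped by visit, assessments will be categorized using visit windows based on study days".

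**Windows before C1D1 (SAP Table 10).** Screening is Days -37 to -17 with no scheduled day (NA). C1D-16 is Day -16 alone. Both hold in every column. C1D-2 (vital signs, ECG) is -15 to -1. The C1D1 window for chemistry, hematology, urinalysis and ECOG is -15 to 3.

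**Choice between visits.** The rule reads: "if more than one visit occurs during a visit window, the visit closest to the scheduled day will be assigned to the windowed visit"; a tie goes to the later one. It covers only windows that begin at "the treatment start date (i.e., Cycle 1 Day -16") or after, up to the post-treatment visit.

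**First dose elsewhere in the SAP.** Section 4.2.1 states: "Cycle 1 Day -16 is used for date of first dose". Section 5.1.1 defines the treatment period for other safety assessments as "between the date of first dose of study drug and the date of last dose of study drug + 29 days". Section 4.2.5 schedules triplicate ECGs on C1D-16 "Predose and at 2 and 6 hours" after the dose.

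**Protocol tolerances (Table 9-1).** Day -2 may move by 1 day either way, and C1D1 may be up to 2 days late. From Cycle 3 the mid-cycle visit is "Day 15 (± 3) [as required in Cycle 5 and beyond"].

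**Cycle 5 hematology (SAP Table 10).** C5D1 is 106 to 126. The general rows are 28(Y-1)-6 to 28(Y-1)+7 for CYD1 and 28(Y-1)+8 to 28(Y-1)+21 for CYD15. Both carry footnote a, whose text is not visible in the copy available. The notes under the table keep two-weekly hematology from Cycle 5 for patients without stable Grade 2 or lower values.

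**The concern.** The pre-treatment windows are counted back from a date that the protocol allows to move, while the C1D-16 window has no tolerance. Any permitted delay therefore moves the first-dose visit across the boundary into Screening. On-treatment records, post-dose ECGs among them, would then carry a pre-treatment label in the by-visit tables, against the SAP's own definitions of first dose and treatment period. Patients who never start daily dosing, whom SAP 4.2.7 provides for, have no Study Day 1 at all.

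The hematology issue is separate. The C5D1 window ends where a four-weekly schedule would end, although the formula rows for that column are two-weekly. The Cycle 5 Day 15 counts come from patients whose hematology has not stabilised, and SAP 5.2.10 plans graphs of neutrophil counts over time, so their placement matters for that display.

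**Working it through.** **Part 1: first-dose day**

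On schedule, C1D1 falls 16 calendar days after the first dose. With C1D1 late by k days:

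- study day of first dose = -(16 + k)
- permitted screening range (21 days before first dose, Protocol 9.1) = -(37 + k) to -(17 + k)

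At k = 0 this reproduces the table: first dose on -16, Screening -37 to -17.

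| C1D1 delay | First dose on study day | Table 10 label | Permitted screening days | Screening days with no window |
|---|---|---|---|---|
| 0 | -16 | C1D-16 | -37 to -17 | 0 of 21 |
| 1 | -17 | Screening | -38 to -18 | 1 of 21 (4.8%) |
| 2 | -18 | Screening | -39 to -19 | 2 of 21 (9.5%) |

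A 1-day delay is consistent with the PK schedule. If Day -2 is 1 day late it falls at first dose + 15 days. Its 48 h sample is then at first dose + 17, which is C1D1 at k = 1. Protocol 8.5.5 places the final PK sample on C1D1. At k = 2, C1D1 is at first dose + 18, so even the latest permitted 48 h sample would come 1 day before it. A 2-day delay is within the C1D1 tolerance but fits the PK schedule less well.

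What moves, per affected patient:

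- Vital signs, ECOG and ECG are always scheduled on the first-dose day. ECGs: 3 time points × 3 = 9 tracings, of which 2 × 3 = 6 are post-dose.
- Chemistry, hematology and urinalysis move only if drawn that day, since Protocol 10.6.2 waives repeats when screening tests are within 7 days.
- One patient is 1/3 = 33% to 1/6 = 17% of the C1D-16 row in a cohort of 3 to 6.

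The closest-visit rule does not help: it starts at C1D-16, and Screening has no scheduled day to measure from.

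**Part 2: Cycle 5 hematology**

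| Y | CYD1 by formula | CYD15 by formula | Explicit rows |
|---|---|---|---|
| 3 | – | 64-77 | C3D15 64-77 (same) |
| 4 | 78-91 | 92-105 | C4D1 78-91, C4D15 92-105 (same) |
| 5 | 106-119 | 120-133 | C5D1 106-126 (differs); C5D15 absent |
| 6 | 134-147 | 148-161 | none |

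The formulas reproduce the explicit C3D15, C4D1 and C4D15 rows but not C5D1. The upper limit 126 fits the four-weekly formula 28(Y-1)-13 to 28(Y-1)+14, whose Y = 6 window starts on 28 × 5 - 13 = 127.

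Scheduled C5D15 is Day 28 × 4 + 15 = 127, so ± 3 gives Days 124 to 130.

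- *Formulas from Y = 5.* Days 120-126 lie in both C5D1 and C5D15. A C5D1 sample on Day 113 ± 3 is at most 3 days from schedule; a Day 124-126 sample is 11 to 13 days away. The closest-visit rule therefore gives C5D1 to the former. The Day 124-126 sample takes C5D15 (1 to 3 days from Day 127). Days 127-130 lie in C5D15 only. Every on-schedule sample has one place.
- *Formulas from Y = 6.* Days 127-133 have no window, including the scheduled C5D15 day. Days 124-126 fall in C5D1 and lose to an on-schedule C5D1 sample.

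**Which start is more natural?** The ECG column has no explicit C4D1 or C5D1 cell, although ECGs are due on Day 1 of each cycle. The ECG formula gives 71-98 at Y = 4 and 99-126 at Y = 5, which continues C3D1 (43-70) exactly. So the formulas appear to fill blank cells, and the blank C5D15 hematology cell would take 120-133. No single start suits all columns, however: the chemistry formula at Y = 5 gives 99-126, which overlaps C4D15 (92-105) on Days 99-105.

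**The case against.** The strongest case against concerns Part 2. A reader might infer that the Cycle 5 window fails whichever Y the formulas start from, and that C5D15 neutrophil counts have no usable or unique place. The documents do not support that. On the more natural reading (Y = 5), the closest-visit rule places every on-schedule sample. Double labelling needs a missing C5D1 sample or an off-schedule draw. The unseen footnote might also restrict the formulas by monitoring schedule, with 106-126 meant for patients monitored monthly. Nothing visible shows this, but it cannot be excluded. What stands is the mismatch between the stated window and the formulas.

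On Part 1, it is fair to say that the number of late patients is unknown, that 2 h and 6 h ECG records under a Screening label would be conspicuous in programming, and that table shells not supplied may deal with display. None of this changes the written rule, which assigns the first-dose visit to Screening after a delay that the protocol permits.

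The objection on severity also stands. Part 1 of the study is descriptive with no formal test, and dose decisions rest with the safety monitoring committee on data from the DLT period.

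**Conclusion.** Table 10 has one clear windowing error and one smaller inconsistency, both of minor severity.

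**Part 1 (high confidence).** A 1-day delay of C1D1 moves the first-dose visit into Screening and empties that patient's C1D-16 row. This follows from the SAP's day count and the protocol's tolerance. The 33% to 17% share is conditional on at least one late patient in a cohort.

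**Part 2 (moderate confidence, because footnote a is not visible).** The C5D1 hematology window contradicts the two-weekly formulas. The likely result is a 7-day overlap (120-126) that rarely matters. Only if the formulas start at Y = 6 does a 7-day gap (127-133) arise.

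A reader might also infer that baseline or the safety conclusions are compromised. They are not. Safety baseline (SAP 4) uses the date and time of first administration. Last, maximum and minimum values use the treatment period, and worst-grade shifts use that baseline and all post-baseline values, scheduled or not. Adverse events and DLTs do not use Table 10, and listings show all data regardless of window. The effect is confined to by-visit tables and figures.

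**What to change.** **Part 1**

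- Assign all assessments on the actual first-dose date, predose and post-dose, to C1D-16, and the 21 days before it to Screening.
- Run C1D-2 (vital signs, ECG) from the day after first dose to the day before actual C1D1.
- Start the C1D1 windows for chemistry, hematology, urinalysis and ECOG on the day after first dose.
- Keep actual C1D1 as the anchor from C1D1 onward.
- For patients who never start daily dosing, window Screening, C1D-16 and C1D-2 from the first-dose date, with C1D-2 at first dose +1 to +15 days (the equivalent of -15 to -1 on schedule). List their later records without placing them in C1D1 or later cycle rows. The post-treatment window, counted from last dose, is unchanged.

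**Part 2**

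- Set C5D1 hematology to 106-119 and add C5D15 hematology as 120-133.
- Apply the hematology formulas from Cycle 6 (134-147 and 148-161). The windows are then contiguous, with no overlap or gap.
- State the range of Y for each column.

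**Cost.** An edit to Table 10 and minor programming, with no new data. For patients with an on-time C1D1, the pre-C1D1 windows stay as they are. Laboratory samples drawn up to 48 hours before the first-dose visit remain in Screening as now and are still available for baseline. Patients monitored monthly would have no scheduled C5D15 sample, as already happens from Cycle 6.

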5.2 Analysis Methods (Part 1)

5.2.1. Patient Disposition

- The number of patients in following categories will be summarized for all screened patients without percentages, only for the overall treatment:
 - Screened patients
 - Screen failures and reasons for screen failure
- The number of patients and percentages will be summarized for all screened patients by treatment for:
 - Enrolled patients
- The number of patients and percentages in the following categories will be summarized based on the safety population by treatment group and overall, unless otherwise specified:
 - Patients treated (safety population)
 - Patients not treated

- Full analysis Set
- Response evaluable analysis set
- Treatment disposition along with reason for discontinuation
- Continued with study survival follow-up at end of treatment
- Study disposition along with the reasons for discontinuation
- Death summary (death and reasons)

Listings will be provided for enrollment information (country, date of protocol version, date of informed consent, and date of first dose), end of treatment disposition, end of study disposition and death.

5.2.2. Protocol Deviations

Protocol deviations will be classified as major or minor for severity based on if they may affect the ability to assess the safety and efficacy of study drug. The classification of protocol deviations will be finalized at the Classification Meeting prior to database lock.

The number and percentage of patients by dose level and overall and deviation type will be presented for all major protocol deviations for safety population. All protocol deviations will be listed including detailed description, deviation type and subtype and classification for major or minor based on data recorded on Protocol Deviation Logs, including unavoidable protocol deviations due to COVID-19 illness and/or COVID-19 control measures, provided by PAREXEL Medical.

5.2.3. Demographic and Other Baseline Characteristics

Demographics – age (at informed consent), sex, child-bearing potential (female patients only), race, ethnicity – and baseline patient characteristics including height (cm), weight (kg), BMI (kg/m^2), and smoking history (history of smoking – Y/N, average packs per day, and years smoking) will be tabulated by dose level and overall, using all patients in the safety population to descriptively assess the comparability of the groups. Body mass index (BMI) (kg/m^2) is calculated by $\text{weight} (\text{kg})/[\text{height} (\text{m})]^2$.

The following baseline lung cancer characteristics will be summarized as continuous or categorical variables, where appropriate:

- Tumor type at initial diagnosis
- Stage of disease at initial diagnosis
- Time from initial diagnosis to first dose day (in months)
- Current status of brain metastases
- EGFR mutation status and the identified mutations

- Eastern Cooperative Oncology Group (ECOG) performance status

All data will be listed for all enrolled patients.

